4.3.2. Secondary and Exploratory Efficacy Endpoints

Secondary and exploratory efficacy endpoints are supportive to the primary hypothesis.

The following secondary and exploratory efficacy binary endpoints will be presented as percentage point estimates and exact 2-sided Clopper-Pearson 95% CIs. Each of the following

endpoints will be analyzed separately based on qualifying lesions present at baseline and for all lesions regardless of presence at baseline, unless otherwise noted.

- Histologic regression of anal or anal/peri-anal HSIL and virologic clearance of HPV-16/18 in intra-anal and/or peri-anal lesion tissue will be assessed at Week 64 for all subjects and also stratified by subjects who receive 3 or 4 doses.
- Histologic regression of anal or anal/peri-anal HSIL or virologic clearance of HPV-16/18 in intra-anal and/or peri-anal lesion tissue will be assessed at Week 36 for all subjects and separately at Week 64 for all subjects and also stratified by subjects who receive 3 or 4 doses.
- Histologic regression of anal or anal/peri-anal HSIL will be assessed at Week 36 for all subjects and separately at Week 64 for all subjects and also stratified by subjects who receive 3 or 4 doses.
- Virologic clearance of HPV-16/18 will be assessed by testing from intra-anal and/or peri-anal lesion tissue at Week 36 for all subjects and separately at Week 64 for all subjects and also stratified by subjects who receive 3 or 4 doses.
- Virologic clearance of HPV-16/18 will be assessed by intra-anal swab testing at Week 36 for all subjects and separately at Weeks 64 and 88 for all subjects and also stratified by subjects who receive 3 or 4 doses.
- Virologic clearance of HPV-16/18 will be assessed on specimens from non-anal anatomic locations as applicable based upon gender (i.e., oropharynx, cervical, vaginal, and penile) at Week 36 for all subjects.
- Complete histopathologic regression of anal or anal/peri-anal HSIL to normal tissue will be assessed at Week 36 for all subjects and separately at Week 64 for all subjects and also stratified by subjects who receive 3 or 4 doses. Normal tissue is defined as having no evidence of anal or anal/peri-anal LSIL or HSIL (AIN2, AIN3, PAIN2, PAIN3).
- Non-progression of anal or anal/peri-anal HSIL will be investigated at Week 36 for all subjects and separately at Week 64 for all subjects and also stratified by subjects who receive 3 or 4 doses. Progression is defined as advancement to carcinoma by histology according to the PAC.

Reduction in surface area of qualifying intra-anal and/or peri-anal lesion(s) at Weeks 36, 64, and 88 will be assessed and determined by quantitative analysis of standardized pre-biopsy digital photographic imaging. The mean percent change and associated 95% t-distribution based CI will be presented. A lesion will be considered qualifying if it is confirmed to be HPV-16 and/or HPV-18 positive and is histologically confirmed as intra-anal and/or peri-anal HSIL by the PAC at Screening.

The relationship between regression/clearance endpoints at Week 36 will be summarized with the number and percentage of subjects meeting the endpoint separately by previous HRA results, previous cytology results, and previous HPV test results. The relationship between the

regression/clearance endpoints at Week 36 with miRNA profiles will be summarized with the median change from baseline in miRNA profiles by those who achieved versus those who did not achieve the endpoint. A subject's miRNA profile is based on change from baseline normalized result to the latest normalized result obtained before the time of the Week 36 endpoint.

By-subject listings will be provided for all efficacy-related parameters and results.

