1.2. Study Design

1.2.1. Synopsis of Study Design

HPV-203 is a Phase 2, open-label efficacy study of VGX-3100 (DNA plasmids encoding E6 and E7 proteins of HPV types 16 and 18) administered by IM injection followed by EP in adult men and women who are HIV negative with histologically confirmed anal or anal/peri-anal

HSIL associated with HPV-16 and/or HPV-18. Approximately 24 subjects will receive at least 3 doses of VGX-3100. Each dose of VGX-3100 will be administered IM in a 1-mL volume followed immediately by EP.

To be eligible for the study, subjects must consent to participate and agree to the collection of anal lesion tissue samples for anal cytology and genotyping, a Digital Anal Rectal Examination (DARE), blood samples for immunologic assessments, high-resolution anoscopy (HRA) and HRA-guided biopsies. All intra-anal and/or peri-anal lesion(s) of adequate size ($\geq 4\text{mm}$) will be biopsied at Screening. Biopsy slides will be sent to a Pathology Adjudication Committee (PAC) for evaluation before enrollment. To be eligible for enrollment, the PAC must assign the diagnosis of anal or anal/peri-anal HSIL (AIN2, AIN3, PAIN2, PAIN3) based on the biopsy sample(s). Subjects must also have intra-anal and/or peri-anal lesion tissue test positive for HPV genotype 16 and/or 18 to be eligible for participation in the study.

Depending upon their disposition with regard to histologic and lesion area changes during the trial, all eligible subjects who consent to participate in the HPV-203 study will receive at least three doses of VGX-3100 (6 mg in 1 mL) administered IM (deltoid, preferred site, or anterolateral quadriceps, alternate site), each followed immediately by EP with the CELLECTRA™ 5PSP device. The first study treatment will be administered on Day 0, the second at Week 4, and the third at Week 12. Partial response to VGX-3100 may still be of medical importance by being able to limit the extent of surgery necessary. For partial responders at Week 36, a fourth dose may be administered at Week 40.

To assess quality of life and related impacts on subjects, PRO instruments will be provided and will include the Short Form Health Survey version 2 (SF-36v2™), the EQ-5D-5L, and 2 additional PRO questions assessing quality of life after surgery or biopsy.

The total duration of the study is up to 10 weeks for the screening period and up to 88 weeks for the treatment and follow-up periods.

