1.2.5. Efficacy, Pharmacokinetic, and Safety Parameters

1.2.5.1. Efficacy Parameters

The primary efficacy endpoint is the proportion of subjects with combined response outcome of histologic regression of anal or anal/peri-anal HSIL and virologic clearance of HPV-16/18 in intra-anal and/or peri-anal lesion tissue at Week 36. Histologic regression is defined as no evidence of anal or anal/peri-anal HSIL on histology. Virologic clearance is defined as no evidence of HPV-16 and/or HPV-18 by specific HPV testing.

Secondary efficacy endpoints are:

- Proportion of subjects with histologic regression at Week 36.
- Proportion of subjects with virologic clearance from intra-anal and/or peri-anal lesion tissue by type-specific HPV testing at Week 36.
- Proportion of subjects with virologic clearance from intra-anal swab by specific HPV testing at Week 36.
- Proportion of subjects with no evidence of anal or anal/peri-anal low-grade squamous intraepithelial lesion (LSIL) or HSIL (i.e. no evidence of AIN2, AIN3, PAIN2, PAIN3) on histology (i.e., biopsies or excisional treatment) at Week 36.
- Proportion of subjects with no progression of anal or anal/peri-anal HSIL to carcinoma from baseline on histology (i.e., biopsies or excisional treatment) at Week 36.
- Proportion of subjects with histologic regression or virologic clearance at Week 36 from intra-anal and/or peri-anal lesion tissue.
- Percent reduction in the number of qualifying intra-anal and/or perianal lesion(s) and the size of peri-anal lesion(s) as determined by the Investigator at Weeks 36, 64, and 88 compared with baseline. Results will also be classified as follows: no clinically significant lesion resolution (reduction in lesion area of 0%-25%), partial lesion area resolution (>25% and <100% reduction) and complete lesion resolution (no visible lesion).

Exploratory efficacy endpoints are:

- Proportion of subjects with histologic regression and virologic clearance at Week 64 by testing from intra-anal and/or peri-anal lesion tissue.
- Proportion of subjects with histologic regression at Week 64.
- Proportion of subjects with virologic clearance by testing from intra-anal and/or peri-anal lesion tissue at Week 64.
- Proportion of subjects with virologic clearance from intra-anal swab by specific HPV testing at Week 64 and Week 88.

- Proportion of subjects with virologic clearance from non-anal anatomic locations at Week 36.

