4.3.1. Primary Efficacy Endpoint

The primary endpoint is the combined response outcome of histologic regression of anal or anal/perianal HSIL and virologic clearance of HPV-16/18 in intra-anal and/or peri-anal lesion tissue at Week 36. Histologic regression is defined as no evidence of anal or anal/peri-anal HSIL on histology. Virologic clearance is defined as no evidence of HPV-16 and/or HPV-18 from intra-anal and/or peri-anal tissue by type-specific HPV testing. A treatment responder is defined as a subject with no histologic evidence of anal or anal/peri-anal HSIL and no evidence of HPV-16 or HPV-18 in anal lesion tissue and who did not receive any non-study treatment of curative intent of intra-anal and/or peri-anal lesions. A treatment non-responder is defined as a subject with histologic evidence of anal or anal/peri-anal HSIL, adenocarcinoma-in-situ, or anal or anal/peri-anal carcinoma, a subject with evidence of HPV-16/18 in anal lesion tissue, or a subject who received non-study treatment of curative intent of intra-anal and/or peri-anal lesions.

Table 2: Definition of Responder and Non-Responder for Primary Endpoint

Responder	Non-Responder

 • No histologic evidence of anal or anal/peri-anal HSIL in qualifying or new lesions AND • Negative PCR for HPV-16 or HPV-18 in anal lesion tissue in qualifying or new lesions AND • No non-study treatment of curative intent of intra-anal and/or peri-anal lesions 	
 • Histologic evidence of anal or anal/peri-anal HSIL, anal adenocarcinoma-in-situ, anal or anal/peri-anal carcinoma in qualifying or new lesions OR • PCR positive for HPV-16 or HPV-18 in anal lesion tissue in qualifying or new lesions OR • Any non-study treatment of curative intent of intra-anal and/or peri-anal lesions

Note: The efficacy time frame is defined by samples obtained any time starting from 14 days before the protocol-specified target date of Week 36. The first such sample determines the histology endpoint. The most recent HPV clearance result before time of the histologic and lesion sample within the time frame determines the HPV clearance endpoint.

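### Intra-anal swab and non-anal virologic clearance are not restricted to subjects HPV-16/18 positive at that site at baseline

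*SAP*

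**What the plan says.** **Definition.** SAP section 1.2.5.1: "Virologic clearance is defined as no evidence of HPV-16 and/or HPV-18 by specific HPV testing". Section 4.3.1 repeats this for lesion tissue: "Virologic clearance is defined as no evidence of HPV-16 and/or HPV-18 from intra-anal and/or peri-anal tissue by type-specific HPV testing". Both describe the result at follow-up. Neither requires an earlier positive result.

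**Denominator.** Section 4.3.2, swab: "Virologic clearance of HPV-16/18 will be assessed by intra-anal swab testing at Week 36 for all subjects and separately at Weeks 64 and 88". Section 4.3.2, non-anal sites (oropharynx, cervix, vagina, penis): "Virologic clearance of HPV-16/18 will be assessed on specimens from non-anal anatomic locations as applicable based upon gender". The non-anal sentence ends by applying the Week 36 analysis to all subjects, so sex is the only stated limit. Section 4.3 places efficacy analyses in the mITT population, which section 2.1 defines by having been dosed at least once. Section 3.8 plans one subset only, three versus four doses.

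**Entry.** Section 1.2.1: "Subjects must also have intra-anal and/or peri-anal lesion tissue test positive for HPV genotype 16 and/or 18 to be eligible". No section of the SAP asks for a positive swab, rinse or genital sample.

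**Status of the endpoints.** Section 1.2.5.1 lists swab clearance at Week 36 as secondary. Swab clearance at Weeks 64 and 88 and non-anal clearance at Week 36 are exploratory. All are reported as proportions with exact two-sided 95% confidence intervals and no test.

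**The concern.** Clearance is a change from infected to not infected, so only a subject infected at a site can show it. Section 1.1.5.3 recognises this: its objective for non-anal locations concerns the clearing of an infection. The definition and denominator in the analysis sections do not carry that condition. A programmer following them would count a subject who is negative at a site on Day 0 and at Week 36 as a success.

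The trial has one arm, so no control group would expose the inflation. A product with no effect at a site would still show clearance there. The exact interval would also look too narrow, because uninfected subjects would be counted as evidence.

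**Working it through.** **1. The plan's own figure.** The SAP gives no expected rate, baseline positivity or precision for these endpoints, so there is nothing to reproduce for them. Its one power statement (section 3.1: 24 enrolled, 90% evaluable, 40% versus 15%, one-sided 0.05) concerns the primary endpoint. It is reproduced. 24 x 0.9 = 21.6, and with 21 evaluable and success at 7 or more responders the exact test has alpha 0.0287 and power 0.7998. This point does not touch that figure.

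**2. Formula.** Let N be the subjects analysed, q the share HPV-16/18 positive at the site at baseline, and c the true clearance among them. Assume no new infections and no missing results.
- Baseline-negative subjects, all still negative and counted as cleared: N(1 - q)
- Baseline-positive subjects who clear: N*q*c
- Reported proportion: (1 - q) + q*c

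Since q*c is at least 0, the result cannot fall below 1 - q.

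**3. Range.** Both q and c are assumed. The 40% column borrows the response rate from section 3.1 for illustration only.

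| q | Reported, c = 0 | Reported, c = 40% |
|---|---|---|
| 10% | 90% | 94% |
| 25% | 75% | 85% |
| 50% | 50% | 70% |
| 70% | 30% | 58% |
| 90% | 10% | 46% |
| 100% | 0% | 40% |

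For example, at q = 70% and c = 40%: 0.30 + 0.70 x 0.40 = 0.58. The reported and true figures agree only when everyone is positive at baseline, or when everyone positive clears.

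**4. Examples with N = 24 (exact 95% intervals).** The full 24 could apply to the swab or the oropharynx; genital sites would have fewer because of the limit by sex.

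| Assumed case | All subjects | Baseline-positive only |
|---|---|---|
| Non-anal site, 6 positive, 0 clear | 18/24 = 75.0% (53.3-90.2) | 0/6 = 0% (0-45.9) |
| Non-anal site, 6 positive, 2 clear | 20/24 = 83.3% (62.6-95.3) | 2/6 = 33.3% (4.3-77.7) |
| Swab, 20 positive, 8 clear | 12/24 = 50.0% (29.1-70.9) | 8/20 = 40.0% (19.1-63.9) |

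**5. Is the baseline result available?** Table 1 (section 1.2.4) appears to schedule the oropharyngeal rinse and genital swabs on Day 0, and the anal swab at Screening and Day 0. The column layout is damaged in the text reviewed, so this should be confirmed against the table itself. Section 3.4 already defines baseline as the last value before first dose.

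**The case against.** No sentence in the SAP says that baseline-negative subjects count as cleared. The reference to all subjects recurs throughout the list in section 4.3.2, usually set against a split by three or four doses, so it may mean only that dose groups are pooled. The word clearance can imply earlier positivity, and the objective in section 1.1.5.3 supports that reading. Section 4.3.2 also plans summaries of the Week 36 endpoints by previous HPV test results, and by-subject listings. Table shells, where denominators are often fixed, are a separate document (section 7.2). Neither they nor the protocol were available.

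Much of this stands. A reader might infer that the sponsor has decided to score uninfected subjects as successes. The text does not show that; it shows a definition and a denominator with the baseline condition missing. The objection does not remove the gap, however. The non-anal item has no dose split for its reference to all subjects to contrast with, and nothing else in the SAP supplies a site-specific denominator. Listings and summaries by earlier HPV results leave the headline proportion unchanged.

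A reader might also infer that the secondary swab result would mostly reflect uninfected subjects. The documents do not support this. Entry requires HPV-16/18 in anal or peri-anal lesion tissue, so a positive swab at baseline is likely to be common, though not certain, for instance when only peri-anal tissue is positive. Very high apparent clearance with no effect, in the region of 75-90%, is a scenario for the exploratory non-anal sites.

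**Conclusion.** The point holds as a gap in the stated definition and denominator. Followed literally, sections 1.2.5.1 and 4.3.2 report (1 - q) + q*c in place of c for the intra-anal swab and each non-anal site. With zero true clearance this is about 75-90% at a non-anal site if 10-25% are positive at baseline, and about 10-30% for the swab if 70-90% are positive. These positivity ranges are assumptions, because the SAP gives none. The actual size at any site is unknown, and new infections would lower the reported figure.

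A reader might go further and doubt the efficacy conclusion. That does not follow. Every subject enters with HPV-16/18 in lesion tissue, and section 4.3.2 makes a positive HPV-16/18 result part of what qualifies a lesion. The primary endpoint, its formal test and lesion-tissue clearance on qualifying lesions are therefore unaffected. The affected endpoints are descriptive: one secondary, the rest exploratory. This should be corrected before the analysis, but it does not undermine the trial.

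**What to change.** In section 4.3.2, for the intra-anal swab and for each non-anal site:
- Set the denominator to mITT subjects positive for HPV-16 and/or HPV-18 at that site at baseline, using the section 3.4 definition.
- Show that number beside each proportion.
- Define clearance as negative for both types at follow-up.
- Report new detections among baseline-negative subjects separately.

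Carry the same wording into section 1.2.5.1 and the table shells. If this restriction is already intended, one sentence saying so is enough.

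The cost is wording, smaller denominators and wider intervals. In the assumed case of 6 positive and 2 cleared, the interval goes from 62.6-95.3% to 4.3-77.7%. Some non-anal sites may have too few positive subjects for a useful estimate, and the report should then say so. No new samples should be needed if the Day 0 collection in Table 1 is as it appears.

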1.1.5.2. Secondary Objectives

The secondary objectives include the following:

- To evaluate the safety and tolerability of VGX-3100 delivered IM followed by EP
- To determine the efficacy of 3 doses of VGX-3100 as measured by histologic regression of anal or anal/peri-anal HSIL
- To determine the efficacy of 3 doses of VGX-3100 as measured by virologic clearance of HPV-16 and/or HPV-18 by testing from lesion tissue
- To determine the efficacy of 3 doses VGX-3100 as measured by virologic clearance of HPV-16 and/or HPV-18 by intra-anal swab testing
- To determine the efficacy of 3 doses of VGX-3100 as measured by complete histopathologic regression of anal or anal/peri-anal HSIL to normal tissue
- To determine the efficacy of 3 doses of VGX-3100 as measured by histopathologic non-progression of anal or anal/peri-anal HSIL
- To describe the efficacy of VGX-3100 for partial responders, as measured by reduction in the number of intra-anal and/or peri-anal lesion(s), as applicable and the reduction in the size of peri-anal qualifying lesion(s), if present, and for whom the disease has not progressed according to Investigator judgment in subjects who did not have anal or anal/peri-anal HSIL lesion resolution at Week 36
- To determine the cellular immune response following administration of VGX-3100 at post dose 3, and after additional dosing compared to baseline

- To determine the efficacy of 3 doses of VGX-3100 with respect to histopathologic regression of anal or anal/peri-anal HSIL or virologic clearance of HPV-16 and/or HPV-18

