5. Negative spot urine pregnancy test is required for female subjects at Screening, before each study treatment, high-resolution anoscopy (HRA), and biopsy/surgical excision; the pregnancy test at Week 40 would only be needed for subjects who receive an additional dose.
6. At least 34 mL (4 x 8.5-mL yellow [ACD] tubes) whole blood and 4 mL serum per time point. At least 68 mL whole blood and 8 mL serum should be collected before first dose.
7. At least 51 mL (6 x 8.5-mL yellow [ACD] tubes) whole blood and 4 mL serum should be collected at Week 15.
8. Digital Anal Rectal Examinations (DARE) are to be performed once cytology has been collected and before HRA.
9. An additional visit may be scheduled to perform HRA if worsening of disease is suspected. Biopsies should not be performed at any visit other than at entry (Screening) and Weeks 36 and 64 for Subgroup C unless the Investigator suspects invasive cancer. All biopsy samples and/or excision samples must be sent to the Pathology Adjudication Committee (PAC) for review.
10. Photography of qualifying lesion(s) must be performed before and after biopsy, and at all HRA examinations. If a pre-biopsy digital photograph is not available for a historical biopsy sample at Screening, a post-biopsy photo will be sufficient. Photographs of intra-anal lesion(s) will be for documentation purposes only. All qualifying peri-anal lesion(s) will be assessed using the ruler provided. The ruler should be placed in the field of vision and should be documented with photography at Screening, Day 0, and Weeks 4, 15, 28, 36, 64, and 88.
11. Tissue specimens (paraffin blocks) from all excised tissue lesion(s) that led to eligibility at study entry must be reviewed by the PAC, and residual tissue from entry and Weeks 36 and 64 specimen(s) (paraffin blocks) must be sent to the central laboratory for immune analysis and Human Papillomavirus (HPV) testing.
12. Potential dosing at Week 40 is applicable for partial responders only.
13. A phone call will be used to review the Participant Diary Card (PDC) with subjects within 8-14 days after doses 1 and 2. The subject will be expected to bring the PDC to the next visits for review. Subjects who receive an additional fourth dose will also have a phone call 8-14 days post dose 4 where the PDC will be reviewed. The subject should bring the PDC to the next visit.

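### Section 4.3.2 analyses photographic area of intra-anal lesions, contrary to the SAP's own endpoint and schedule, and specifies no summary of lesion count

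*SAP*

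**What the plan says.** The secondary objective in section 1.1.5.2 describes partial response through "reduction in the number of intra-anal and/or peri-anal lesion(s), as applicable and the reduction in the size of peri-anal qualifying lesion(s), if present". Its target group is subjects whose disease has not progressed in the Investigator's judgment, and it applies "in subjects who did not have anal or anal/peri-anal HSIL lesion resolution at Week 36".

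The matching endpoint in 1.2.5.1 is "Percent reduction in the number of qualifying intra-anal and/or perianal lesion(s) and the size of peri-anal lesion(s) as determined by the Investigator". It is assessed against baseline at Weeks 36, 64 and 88. Results are also to be put into three classes. The lowest is "no clinically significant lesion resolution (reduction in lesion area of 0%-25" percent). The other two are "partial lesion area resolution (>25% and <100% reduction) and complete lesion resolution (no visible lesion").

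Table 1 note 10 (section 1.2.4) covers the images. On intra-anal lesions it says: "Photographs of intra-anal lesion(s) will be for documentation purposes only". On peri-anal lesions it says: "All qualifying peri-anal lesion(s) will be assessed using the ruler provided", with the ruler visible in the photograph.

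Section 4.3.2 then gives the analysis: "Reduction in surface area of qualifying intra-anal and/or peri-anal lesion(s) at Weeks 36, 64, and 88 will be assessed and determined by quantitative analysis". The images are standardised digital photographs, and the result is reported as a mean percent change with a t-based 95% CI. Section 5 declares no departure from the protocol-defined analyses.

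**The concern.** The analysis section differs from the endpoint it serves in three ways: which lesions are sized, whether lesions are counted, and who or what makes the measurement. Section 5 does not present this as a deliberate change.

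Partial response is a substantive question in this trial, since 1.2.1 says it may matter for limiting the extent of surgery. Eligibility admits anal HSIL without peri-anal disease, so some subjects may have intra-anal lesions only. For them the endpoint offers count and no size measure. Section 4.3.2 offers size and no count.

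The programmer would have to choose between measuring intra-anal photographs despite note 10 and quietly restricting the analysis to peri-anal lesions under a label that claims both. In an open-label, single-arm trial of about 24 subjects, that choice should not be left until the data are visible.

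**Working it through.** The SAP gives no figure on this point to reproduce. The power statement in 3.1 concerns the primary test and has no bearing here. The check is a comparison of sections.

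| Place in SAP | Lesions counted | Lesions sized | Source |
|---|---|---|---|
| 1.1.5.2, objective | intra-anal and/or peri-anal | peri-anal only | Investigator judgment named for progression |
| 1.2.5.1, endpoint | intra-anal and/or peri-anal | peri-anal only | Investigator |
| Table 1 note 10 | not addressed | peri-anal, with ruler in the photograph | intra-anal photographs not for measurement |
| 4.3.2, analysis | none specified | intra-anal and/or peri-anal | quantitative photograph analysis |

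1. **Scope of size.** The first three rows agree with one another. Section 4.3.2 stands alone in sizing intra-anal lesions, and the SAP describes no other intra-anal size measurement.

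2. **Count.** The bullets of 4.3.2 cover binary histologic and virologic endpoints, and the lesion paragraph covers area. None gives a summary for count, a table of the three classes, or a restriction to subjects unresolved at Week 36.

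3. **Classification.** Let A0 be the baseline area and A1 the later area, so the percent reduction is R = 100 x (A0 - A1)/A0. The classes are R from 0 to 25, R above 25 and below 100, and no visible lesion. If A1 exceeds A0, R is negative and no class applies. The first two classes are also defined on area. A subject with intra-anal lesions only, and so without a usable area, can be placed only if no lesion is visible.

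4. **Size of the effect.** Let k be the number of the 24 planned subjects with a qualifying peri-anal lesion. The SAP does not state k. The area analysis that matches the endpoint rests on at most k subjects, and the other 24 - k can contribute only a count. Taking k as an assumption, and ignoring dropout:
   - k = 24: 24 - 24 = 0 subjects depend on count alone.
   - k = 12: 24 - 12 = 12 subjects, half the sample.
   - k = 6: 24 - 6 = 18 subjects, or 18/24 = 75%.
   - k = 0: all 24, and no area analysis is possible.

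   The half-width of the planned t interval, in units of the SD of percent change, is t(0.975, k - 1)/sqrt(k). This is 2.069/4.899 = 0.42 at k = 24, 2.201/3.464 = 0.64 at k = 12, and 2.571/2.449 = 1.05 at k = 6. A table that does not show k would hide this difference.

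**The case against.** The best defence is that nothing has been removed. The count endpoint stands in 1.2.5.1 with its metric, visits and comparator, and the same bullet commits to the classification. Section 3.2 promises tabulations of efficacy parameters, with n and percent for categorical variables and n, mean, median, SD and range for continuous ones. Section 4.3.2 lists all efficacy results by subject. The table shells are a separate document not at hand and may contain a count table. This stands in part. A reader might infer that the count endpoint is dropped or that the partial-response question goes unanswered, and the SAP does not support either. What remains is that 4.3.2 sets out methods for the other secondary endpoints and leaves count to a default, with no CI and no stated population.

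Three other strong readings also fail:

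- A reader might say the schedule states that intra-anal area is not measured. Note 10 limits the purpose of the photographs and says no more than that. The conflict with 4.3.2 is real all the same.
- A reader might conclude that photograph analysis is wrong for peri-anal lesions and that ruler readings must replace it. Note 10 puts the ruler in the photographed field, so ruler-scaled photographs are compatible with it. The SAP does not say that a separate ruler-based area is recorded.
- A reader might conclude that enlarging lesions disappear from the analysis. Growth still enters the mean percent change, so the gap is confined to the classification. The objective also excludes subjects who progressed in the Investigator's judgment, so some enlarged lesions may lie outside its target group.

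Finally, the objective is descriptive, secondary endpoints are called supportive, and only the primary endpoint is formally tested. That limits the weight of the point. It does not remove the contradiction.

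**Conclusion.** The point holds as an inconsistency in a secondary analysis. Section 4.3.2 sizes intra-anal lesions from photographs, against the objective, the endpoint and Table 1 note 10. It also specifies no analysis for count, the only component that reaches subjects with intra-anal lesions alone, and the classification has no place for growth.

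The number of subjects affected depends on how many have qualifying peri-anal lesions. That number is not given, so the values of k above are illustrations and not estimates. The conclusion does not depend on k, except that if every subject had peri-anal lesions, none would rely on count alone.

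The effect is confined to a descriptive secondary endpoint. The primary test and its success criterion are unaffected. The point should be corrected before database lock.

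**What to change.** Revise 4.3.2 as follows:

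- **(a) Count.** Summarise percent change from baseline in the number of qualifying lesions at Weeks 36, 64 and 88, for all mITT subjects with data, with a CI. The exact non-parametric interval on the median, already used in 4.3.3 and 4.3.4, would suit a coarse percentage.
- **(b) Area.** Restrict it to subjects with qualifying peri-anal lesions and show that n in every table. Reconcile Investigator determination (1.2.5.1) with photograph analysis (4.3.2) by naming one measurement source. Ruler-scaled photographs would agree with note 10.
- **(c) Classification.** Tabulate it with an added category for increase in area, and show how many subjects have no area measurement. This is a reporting category only and implies nothing about dosing.
- **(d) Target group.** Present (a) to (c) also for the group in the objective: no lesion resolution at Week 36 and no progression in the Investigator's judgment.

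The cost is SAP wording and table shells. The endpoint already calls for count and peri-anal size, so no new assessment should be needed, provided the chosen source in (b) is one already being recorded.
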